7.6 Overall Survival

The OS is defined as time from the first day of treatment to the date of death. A subject alive at the end of study or lost to follow-up will be censored for OS at the last date when the subject was known to be alive, i.e., the last date on study.

If data warrants, the median and quartiles of OS and their 95% CIs will be assessed using the Kaplan-Meier method and Brookmeyer and Crowley method, respectively. The proportion of subjects alive at 12 weeks, 24 weeks, 48 weeks, 72 weeks, and other timepoints of interest will be estimated using the Kaplan-Meier method. OS will be summarized and listed for the All Treated population.

7.7 Exploratory Analysis

Exploratory analyses of ORR, CBR, TTR, DOR and PFS will be based on the investigator disease assessment per iRECIST (iORR, iCBR, iTTR, iDOR and iPFS).

Shattuck labs, Inc SL-172154

17January2023

Disease response will be evaluated and documented in CRF based on RECIST 1.1 until the first PD per RECIST 1.1, and then will be evaluated and documented in CRF based on iRECIST. The iRECIST responses at the timepoint assessments before and on the assessment of first PD per RECIST 1.1 are derived based on RECIST 1.1 assessment as in Table 5.

Table 5. Derivation of iRECIST response for assessments before or on PD per RECIST 1.1

Timepoint response per RECIST	Timepoint response per iRECIST
CR	iCR
PR	iPR
SD	iSD
PD	iUPD
NE	iNE

If data warrants, analysis of iORR, iCBR, iTTR, iDoR, and iPFS based on iRECIST will be performed similarly as those based on RECIST 1.1 (Section 7.1, 7.2, 7.4 and 7.5) except the following:

- The best overall response based on iRECIST (iBOR) is defined as the best overall response among all post-baseline timepoint assessments until the first confirmed PD per iRECIST (iCPD) or the last disease assessment if an iCPD has not been observed.
- The TTR based on RECIST 1.1 (iTTR) is defined as the time from the first dose until the first documentation of a subsequently confirmed objective response per iRECIST (iCR or iPR). Only subjects who have achieved objective response (iCR or iPR) will be evaluated for iTTR.
- The DOR based on iRECIST (iDOR) is defined as time from the date of the first iCR or iPR (confirmed at least 28 days later) to the date of the first documented iUPD that was subsequently confirmed as CPD or death due to any cause, whichever occurs first. Only subjects who have achieved objective response (iCR or iPR) will be evaluated for iDOR.
- PFS based on iRECIST (iPFS) is defined as time from the first day of treatment to the first documented iUPD that was subsequently confirmed as iCPD or death due to any cause, whichever occurs first.
- The following will be applied for both iPFS and iDOR:
 - If an unconfirmed PD per iRECIST (iUPD) occurs but is disregarded because of later iSD, iPR or iCR, then the iUPD date should not be used as the progression event for iPFS/iDOR.
 - If an iUPD is not confirmed and there is no subsequent iSD, iPR or iCR, then the iUPD date should still be used as progression event for iPFS/iDOR.
 - If an iUPD is not confirmed and the next timepoint responses are iUPDs but are not confirmed, then the last iUPD of the sequential iUPDs will be used as progression event for iPFS/iDOR.
 - Subjects who have not progressed at the time of analysis will be censored at their last evaluable iRECIST assessment.

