3.5.1 Prohibited Medications/Treatments

Subjects must be instructed not to take any medications, including over-the-counter products without first consulting with the investigator. The following medications are prohibited during SL-172154 therapy:

- Any investigational anti-cancer therapy not described in this protocol
- Any concurrent chemotherapy, radiotherapy (except palliative radiotherapy after consultation with the Sponsor Medical Monitor), hormonal or hormonal suppression therapy for anti-cancer intent, immunotherapy, or biologic therapy for cancer treatment
- Immunosuppressive medications for primary prophylaxis against IRRs are not permitted. Subjects who require immunosuppressive medications (e.g., corticosteroids) for management of irAEs or IRRs should be managed per Toxicity Management Guidelines in Section 3.6.
- Live attenuated vaccines during the study through 30 days after the last dose of SL-172154

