8. ANTI-TUMOR ACTIVITY ASSESSMENTS

Although the clinical benefit of SL-172154 has not yet been established, the intent of offering this IP is to provide a possible therapeutic benefit, and thus the participant will be carefully monitored for tumor response and symptom relief in addition to safety and tolerability. For the purposes of this study, participants should be evaluated for response as outlined in the SOA. Confirmatory scans should be performed at least 4 weeks (>28 days) after initial documentation of an objective response or progressive disease. All participants who underwent the first post baseline disease assessment at the 8-week time point or progress or die before to the first post baseline disease assessment will be considered evaluable for response.

Assessments must be performed on a calendar schedule and should not be affected by dose interruptions or delays. Refer to the SOA (Section 6) for the schedule of disease assessments. More frequent disease assessments may be performed at the discretion of the investigator. For subjects whose disease may be followed by well-characterized tumor markers (i.e., CA-125), disease assessments should include results of tumor marker assessments. If study treatment is withdrawn for reasons other than disease progression, radiographic disease assessments should continue as per the SOA until documented disease progression, the start of new anti-cancer therapy, withdrawal of consent or death. See Sections 8.2 for criteria for continuing treatment past disease progression.

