6.9 Concomitant Procedure

Concomitant procedures include cancer-related or treatment-related procedure or palliative radiotherapy. Concomitant procedures along with start/end date, and indication for the procedure will be presented in a data listing.

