7.1 Objective Response Rate

The ORR is defined as the proportion of subjects whose best overall response is a confirmed CR or confirmed PR based on investigator assessment according to RECIST 1.1. The ORR will be estimated with a 95% CI using the exact probability method. The number and percent of subjects with the best overall response of CR, PR, SD, PD and not evaluable (NE) will be summarized.

Summary of objective response will be provided for the All Treated population and Response Evaluable population, respectively.

The best overall response based on RECIST 1.1 is defined as the best overall response among all post-baseline time point assessments until the first PD per RECIST 1.1 or start of new anti-cancer therapy, whichever is earlier. For subjects who have not met the criteria for PD per RECIST1.1 or have not started a new anti-cancer therapy, the best overall response is defined as the best overall response among all post-baseline timepoint assessments.

Based on the investigator assessment of overall response per RECIST 1.1 at post-baseline assessments, the best overall response will be determined programmatically as the following and Table 3:

- CR > PR > SD > PD > NE
- CR = at least two determinations of CR with at least 4 weeks apart before progression.
- PR = at least two determinations of PR or better with at least 4 weeks apart before progression (and not qualifying for CR).
- SD = at least one SD or better ≥ 49 days after the first dose and before progression (and not qualifying for a CR or PR). The minimum interval from the first dose date for the best response of SD is 8 weeks minus 7 days to allow for visit windows of ± 7 days (49 days).
- If the minimum interval for SD is not met, the best response will depend on the subsequent assessments. See table below for details.
- PD is considered the best overall response when PD is documented and a best overall response of CR, PR, or SD could not be established before documentation of PD. Clinical deterioration will not be considered as documented disease progression in the determination of the best overall response.
- NE is considered the best overall response when PD has not been documented and a best response of CR, PR or SD could not be established.

Table 3. Best overall response when confirmation of CR and PR required.

Overall response First time point	Overall response Subsequent time point	BEST overall response
CR	CR	CR
CR	PR	SD, PD or PR ^a

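### SAP 7.7 drops the stop at new anti-cancer therapy from iRECIST best response, so scans taken on a later regimen can count in the exploratory iRECIST endpoints

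*SAP*

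**What the plan says.** **RECIST 1.1.** SAP 7.1 takes best overall response "among all post-baseline time point assessments until the first PD per RECIST 1.1 or start of new anti-cancer therapy, whichever is earlier". Table 4 in SAP 7.5 censors PFS at the last evaluable assessment before new therapy when that therapy precedes documented progression. SAP 7.4 uses the same censoring for DOR.

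**iRECIST.** SAP 7.7 says these analyses "will be performed similarly as those based on RECIST 1.1 (Section 7.1, 7.2, 7.4 and 7.5) except the following". The first listed exception is iBOR, defined as the "best overall response among all post-baseline timepoint assessments until the first confirmed PD per iRECIST (iCPD) or the last disease assessment" where no iCPD has been observed. Later bullets cover iPFS and iDOR. If an iUPD "occurs but is disregarded because of later iSD, iPR or iCR, then the iUPD date should not be used as the progression event", it is dropped. An unconfirmed iUPD with no later iSD, iPR or iCR keeps its date as the event. Subjects without progression are censored at their last evaluable iRECIST assessment. None of these bullets mentions new therapy.

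**Scans after progression.** Protocol Section 8 states: "Confirmatory scans should be performed at least 4 weeks (>28 days) after initial documentation of an objective response or progressive disease". Appendix 16.5.3 places confirmation of an iUPD 4 to 8 weeks later, and Protocol 6.8 continues assessments until progression is confirmed.

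**Waterfall plot.** SAP 7.1 takes best percent change over all post-baseline assessments up to and including first PD, with no stop at new therapy.

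**Palliative radiotherapy.** The prohibited list in Protocol 3.5.1 includes "radiotherapy (except palliative radiotherapy after consultation with the Sponsor Medical Monitor". SAP 6.9 states: "Concomitant procedures include cancer-related or treatment-related procedure or palliative radiotherapy". It provides a listing of dates and indication.

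**The concern.** The iRECIST endpoints are meant to describe the activity of SL-172154 given alone. Because 7.7 restates the iBOR window as an exception to 7.1, a programmer would not inherit the stop at new therapy. Stability or shrinkage on the next regimen could then be recorded as iRECIST benefit from SL-172154, and an observed progression could be removed from iPFS or iDOR. Anti-tumor activity is one input to selection of the RP2D (Protocol 3.1.1 and Section 2), and only about 6 to 12 subjects are expected at that dose, so a single misclassified subject would be visible.

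**Working it through.** The plan gives no numerical result to reproduce here. The check compares the rules and then gives a scale for one affected subject.

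**1. Windows side by side**

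| Rule | Ends at PD | Ends at new therapy |
|---|---|---|
| RECIST BOR (7.1) | first PD | yes |
| iBOR (7.7) | iCPD, or last assessment | not stated; replaces the 7.1 rule |
| PFS, DOR (7.5 Table 4, 7.4) | first PD | yes, by censoring |
| iPFS, iDOR (7.7) | iUPD later confirmed, or not reset | not in the bullets; apparently carried over from 7.4 and 7.5 |
| Waterfall (7.1) | first PD | not stated |

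**2. Route.** Subjects who stop drug before progression are scanned only until progression or new therapy (Protocol 8.1, SAP 7). After progression, a confirmatory scan is asked for 4 to 8 weeks later, and no text exempts a subject already on another regimen. With an iUPD at the week 8 scan, confirmation falls at weeks 8 + 4 = 12 to 8 + 8 = 16.

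**3. iPFS in that sequence.** Assume an iUPD at week 8, new therapy shortly after, and iSD at week 12.
- Without the week 12 scan, the unconfirmed iUPD stays the event, dated week 8.
- With it, if iUPD counts as documented PD, therapy came after PD. Table 4 censoring is not triggered, the reset removes the event, and the subject is censored at the last evaluable iRECIST assessment, which is the post-therapy scan.
- With it, if iUPD does not count as documented PD, Table 4 censors at the last evaluable scan before therapy, week 8. No progression-free time is added.

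On both readings the event is lost. The same logic applies to iDOR.

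**4. What one late scan can do to response**
- iBOR: SD needs one assessment at least 49 days after first dose (7.1). Weeks 12 to 16 are days 84 to 112, so one post-therapy iSD suffices.
- iCBR: 7.2 uses 15 weeks (16 less a one-week window). A post-therapy iSD at week 15 or later would meet that threshold, although the 7.2 grid has no row for iUPD followed by iSD.
- iORR: response needs two determinations at least 4 weeks apart. One post-therapy scan completes a response only if an iPR or iCR was seen earlier; otherwise two are needed.

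**5. Scale of one misattributed response.** Assumption: 0 versus 1 responder, with exact (Clopper-Pearson) 95% intervals. The rate is 1/n. The upper limit for 0/n is 1 − 0.025^(1/n). For 1/n the lower limit is 1 − 0.975^(1/n), and the upper limit is the 0.975 quantile of Beta(2, n − 1). Planned totals are 21 + 6 + 6 = 33 and 42 + 6 + 6 = 54.

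| n | 0 responders | 1 responder |
|---|---|---|
| 6 | 0% (0 to 45.9) | 16.7% (0.4 to 64.1) |
| 12 | 0% (0 to 26.5) | 8.3% (0.2 to 38.5) |
| 33 | 0% (0 to 10.6) | 3.0% (0.1 to 15.8) |
| 54 | 0% (0 to 6.6) | 1.9% (0.0 to 9.9) |

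**The case against.** **The carry-over clause already supplies a cut-off.** For iPFS and iDOR this is largely right. No bullet in 7.7 cancels the Table 4 censoring, so little or no progression-free time is gained. What remains is that the order of the reset and censoring rules is not stated, and that an event becomes a non-event either way (working, item 3). The clause does not help iBOR, which 7.7 redefines explicitly.

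**The route is narrow.** This also stands. Subjects treated beyond progression remain barred from other anti-cancer therapy (Protocol 3.5.1), scans before progression end at new therapy, and SAP Section 7 mentions confirmatory scans only for response. The post-progression confirmatory scan in Protocol Section 8 still leaves a route open, and one such scan will seldom create an iORR responder.

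**Stronger readings.** A reader might infer that the secondary RECIST ORR, CBR, DOR and PFS are inflated by the same gap. They are not: BOR runs only "until the first PD per RECIST 1.1 or start of new anti-cancer therapy, whichever is earlier", and Table 4 covers PFS and DOR. A reader might also infer that palliative radiotherapy is classed as something other than new anti-cancer therapy and so never ends response assessment. SAP 6.9 only defines a listing category, and the SAP leaves new anti-cancer therapy undefined. Elsewhere radiation is treated as anti-cancer therapy (Protocol 4.1 criterion 11, Protocol 4.2 washout table, SAP 6.6). The plan is silent on this point.

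**Conclusion.** The gap in the iBOR definition is certain from the text. It lets post-therapy scans count towards iBOR, iORR and iCBR, and it leaves a post-therapy iSD, iPR or iCR able to cancel an iUPD in iPFS and iDOR. It reaches only exploratory endpoints, which are analysed where the data support it.

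The actual bias cannot be computed, because the documents give no frequency of scans after new therapy. The figures of 8.3 to 16.7 points at the potential RP2D, and 1.9 to 3.0 points overall, assume exactly one misattributed response. The plan permits such crediting; nothing shows that it occurs.

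The waterfall rule has the same omission with less exposure, since it already stops at first PD and scans before PD are meant to end at new therapy.

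Radiotherapy is a point for clarification only. No response rule in SAP 7.1 to 7.5 addresses a target lesion irradiated after baseline. Appendix 16.5.1 covers previously irradiated lesions without saying what happens to one treated on study.

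**What to change.** In SAP 7.7:
- End iBOR at the earliest of iCPD, start of new anti-cancer therapy, or last disease assessment.
- State that an assessment after new therapy can neither confirm nor reset an iUPD. An iUPD before new therapy with no earlier reset then remains the iPFS/iDOR event. Otherwise the Table 4 new-therapy censoring applies to both endpoints.

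In SAP 7.1, add the same stop to best percent change for the waterfall plot.

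As a clarification, define new anti-cancer therapy for the analysis, say whether on-study palliative radiotherapy counts, and say how a target lesion irradiated after baseline is evaluated.

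The cost is SAP wording and derivation code. The date of first subsequent therapy is already collected (SAP 3.5). A few late scans are excluded, so a delayed effect of SL-172154 first seen after a switch would not be counted. The irradiated site may need a data query, because SAP 6.9 names only dates and indication.

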When using iRECIST, the definitions of measurable and non-measurable lesions still follow RECIST v1.1. The principles used to establish an objective tumor response when using iRECIST are largely unchanged from RECIST v1.1, however, responses assigned using iRECIST have a prefix of "i" (e.g., "immune" complete response [iCR]) to differentiate them from responses assigned using RECIST v1.1.

CONFIDENTIAL Compound: SL-172154

The major change is the concept of resetting the bar if RECIST v1.1 progression is followed at the next assessment by tumor shrinkage. This adaptation accounts for instances where an increase in tumor burden, or the appearance of new lesions, does not reflect true tumor progression. Therefore, iRECIST requires confirmation of progression.

Confirming Progression: iRECIST requires the confirmation of progression and uses the terms iUPD (unconfirmed progression) and iCPD (confirmed progression). Confirmatory scans should be performed at least 4 weeks, but no longer than 8 weeks after iUPD. iCPD is confirmed if further increase in tumor burden, compared to the last assessment, is seen as evidenced by one or more of the following criteria:

- Continued increase in tumor burden (from iUPD) where RECIST v1.1 definitions of progression had been met (from nadir) in target, non-target disease or new lesions.
 - Progression in target disease worsens with an increase of at least 5 mm in the absolute value of the sum
 - Continued unequivocal progression in non-target disease with an increase in tumor burden
 - Increase in size of previously identified new lesion (s) (an increase of at least 5 mm in the absolute value of the sum of those considered to be target new lesions) or additional new lesions
- RECIST v1.1 criteria are met in lesions types (target or non-target or new lesions) where progression was not previously identified, including the appearance of additional new lesions.
- If iUPD is not confirmed at the next assessment, then the appropriate response will be assigned (iUPD if the criteria are still met, but no worsening, or iSD, iPR or iCR if those criteria are met compared to baseline).

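### SAP 7.7 dates a run of unconfirmed iRECIST progressions at its last scan but confirmed progression at its first, so the less certain progressor gets the later iPFS/iDOR event

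*SAP*

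**What the plan says.** SAP 7.7 (Exploratory Analysis) derives iPFS and iDOR from iRECIST, under which progression at one scan is unconfirmed (iUPD) until a later scan confirms it (iCPD). Four rules set the event date:

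- **Confirmed progression.** iPFS ends at the "first documented iUPD that was subsequently confirmed as iCPD or death due to any cause". iDOR ends at "the first documented iUPD that was subsequently confirmed as CPD or death due to any cause, whichever occurs first".
- **Reset.** An iUPD drops out if it "is disregarded because of later iSD, iPR or iCR, then the iUPD date should not be used as the progression event".
- **Unconfirmed, no recovery.** With no later iSD, iPR or iCR, "the iUPD date should still be used as progression event for iPFS/iDOR".
- **Run of unconfirmed iUPDs.** Where the scans that follow are again scored iUPD and none is ever confirmed, the rule is: "then the last iUPD of the sequential iUPDs will be used as progression event for iPFS/iDOR".

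The SAP gives neither an order of precedence between the last two rules nor a reason for choosing the last scan. Runs of this kind can occur: under Protocol 16.5.3, a subject who still meets the progression criteria without further worsening is scored iUPD again.

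**The concern.** There are two separate difficulties.

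First, the last two rules overlap. Take a subject with iUPD at several consecutive scans and no recovery. Applied to the first iUPD, the third rule gives that date, while the fourth gives the last. Two programmers could follow the SAP and derive different event dates.

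Second, whichever rule is meant to win, the fourth sits badly with the definition. A subject whose progression is confirmed is dated at the first iUPD. A subject with the same first iUPD whose progression is never confirmed is dated at the last. Weaker evidence of progression therefore earns a longer iPFS or iDOR.

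What is at stake is how the planned iRECIST results are read. SAP 13.2 lists one Kaplan-Meier figure (14.2.6) covering PFS by RECIST 1.1 and by iRECIST. A reader would naturally take a gap between the two as tumours that grew and then shrank. Under the run rule, part of that gap can come from the dating convention alone.

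**Working it through.** The plan states no figure for this rule, so there is nothing to reproduce. The check applies the dating rules to response sequences on the planned scan schedule.

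**Inputs**
- Scans every 8 weeks to week 24, every 12 weeks to year 2, then every 6 months (SAP 7).
- Confirmatory scan 4 to 8 weeks after iUPD (Protocol 16.5.3).
- Time to event = event date − first dose date + 1; months = days / 30.4375 (SAP 5.3.3).

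A scan at week *w* falls 7*w* days after the first dose, so time = 7*w* + 1 days:
- week 8: 57 days, 57/30.4375 = 1.9 months
- week 12: 85 days, 2.8 months
- week 16: 113 days, 3.7 months
- week 24: 169 days, 5.6 months
- week 36: 253 days, 8.3 months

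**Event date by sequence** (no iSD, iPR, iCR or death; illustrative)

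| Sequence | First iUPD of run | Last-iUPD rule |
|---|---|---|
| iUPD wk 8, iCPD wk 16 | wk 8 (definition) | not applicable |
| iUPD wk 8 and 16, iCPD wk 24 | wk 8 (definition) | not applicable |
| iUPD wk 8 only | wk 8 | wk 8 |
| iUPD wk 8 and 12 | wk 8 | wk 12 |
| iUPD wk 8 and 16 | wk 8 | wk 16 |
| iUPD wk 8, 16 and 24 | wk 8 | wk 24 |
| iUPD wk 24 and 36 | wk 24 | wk 36 |

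**Inversion.** Two subjects both have iUPD at weeks 8 and 16. If week 24 is iCPD, the event is at day 57. If week 24 is another unconfirmed iUPD, it is at day 169. The difference is 169 − 57 = 112 days, or 16 weeks, in favour of the subject whose disease did not worsen enough to be confirmed. The second row takes iCPD at week 24 as confirming the run that began at week 8. The inversion does not depend on that reading: in the two-scan case, iUPD then iCPD gives week 8, and iUPD then iUPD gives week 16.

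**Comparison with RECIST 1.1.** SAP 7.5 dates PFS at the first documented PD, and SAP Table 5 maps that PD to iUPD. With iUPD at weeks 8, 16 and 24, PFS is 8 weeks and iPFS is 24 weeks, with no shrinkage at any scan. If the run were dated at its first iUPD, both would be 8 weeks, and iPFS would exceed PFS for a progressor only where a later iSD, iPR or iCR had reset the iUPD.

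**Step per extra scan.** When the confirmatory window is met, each further unconfirmed scan moves the event by 4 to 8 weeks. The week 24 to week 36 case, a 12-week step, arises only if that window is missed in the 12-weekly phase.

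**The case against.** The strongest reply is that the two bullets do not conflict. The third rule speaks of a single iUPD; the fourth follows it directly and names a narrower case. On an ordinary reading the specific rule governs that case, and otherwise it would never have any effect. This stands: a reader might infer a flat contradiction, but the text shows only overlap without stated precedence. It leaves the inversion against confirmed progressors untouched.

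A reader might also infer that iPFS and iDOR are biased upward. The documents do not establish that. There is no comparator, a never-worsening run is a weaker form of progression, and no passage prescribes the first iUPD for a run that is never confirmed. The protocol's instruction in 16.5.2 to use the earlier date applies to RECIST 1.1 and only once progression is confirmed. What can be said is that the dates are later than under a first-iUPD rule.

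A third tempting inference is that the event date depends on how long treatment continued past progression. Protocol Sections 6 and 8 make assessments calendar-based, and 6.8 continues them until progression is confirmed; Protocol 8.1 and SAP 7 say only until progression. The number of scans after the first iUPD matters, but a link from that number to treatment duration is not documented.

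Finally, the affected group is small. Confirmation has a low threshold under Protocol 16.5.3 (a further 5 mm in the target sum, for example, or any additional new lesion), so repeated iUPD without confirmation, recovery or death should be uncommon. For iDOR the subject must first respond. As an assumption only, the protocol's background rates for another anti-CD47 antibody (5% in solid tumours, Section 1.4.2; 2 of 13 in ovarian cancer, Section 1.3) applied to 33 to 54 subjects give roughly 0.05 × 33 ≈ 2 to (2/13) × 54 ≈ 8 responders. All of this stands and limits the size of the point.

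**Conclusion.** The point holds as a minor one. SAP 7.7 treats confirmed and never-confirmed progression asymmetrically without giving a reason, and the run rule overlaps the bullet before it without precedence. In the worked example the date moves by 16 weeks for one subject.

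This rests on runs of two or more unconfirmed iUPDs occurring, which the protocol permits but whose frequency the documents do not give. The reach is narrow. iPFS and iDOR are exploratory and conditional on the data, RECIST 1.1 PFS and DOR are dated separately, and no dose-escalation, safety or sample-size rule uses these dates. Subject-level listings of iRECIST responses and iPFS are planned (SAP 13.3, listings 16.2.6.4.2 and 16.2.6.6.2), so either date could be recovered afterwards.

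**What to change.** Replace the last-iUPD bullet in SAP 7.7 with: *for an uninterrupted run of iUPDs with no intervening iSD, iPR or iCR, the first iUPD of the run is the progression event date*, for both iPFS and iDOR. This removes the overlap with the bullet before it and puts confirmed and unconfirmed runs on the same footing.

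If the sponsor intends the last iUPD, the SAP should say that this rule takes precedence, give the reason, and add the first-iUPD date as a sensitivity analysis.

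The preferred change costs one sentence in the SAP and a small edit to the derivation. It needs no new data and no protocol amendment.
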